4.3 Interim analyses and data monitoring

Regular monitoring of safety data collected during clinical studies will be performed as described in the Safety Signal Detection in the Ongoing Clinical Trials Charter for CZP.

A specific data monitoring, steering, or evaluation committee is not planned for this study.

An interim analysis is planned to be conducted after the last subject has completed the Week 48 assessment. That is when each treated subject has completed the Week 48 Visit, or withdrawn prematurely. All data collected until the database cut-off date will be included. With this interim analysis, first study results will be available already about one year before the final analysis of the study. There is no intention to stop the study early for efficacy or for futility. The interim summaries and listings will be based on the same shells as for the final analysis, unless otherwise stated. The interim listings will include all data collected up to Week 48. The summary tables presenting results by visit will only consider results up to Week 48 Visit for the interim analysis. Summary tables of results not provided by visit, e.g. adverse events, will not include events or medication that started after the Week 48 Visit. Data collected after Week 48 will not be presented in the interim analysis.

The length of pre-study period and on-study period for collection of AU flares data will be 48 weeks for the interim analysis, and will be 96 weeks for the final analysis. The analysis based on period length of 48 weeks will be repeated for the final analysis.

No separate SAP will be created for the interim analyses, as all analyses will be covered within this SAP, and within the corresponding display specifications. In general, the interim analysis will follow the same specifications as the final analysis, unless stated differently in the corresponding sections. The interim analysis will include a subset of tables and listings that will be marked in the display specifications.

An additional interim data-cut might be needed to support a regulatory submission in nr-axSpA or axSpA.

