10.1 Extent of exposure

The number of doses received will be summarized with continuous statistics for the SS.

Duration of exposure to study medication will be calculated as:

$$Dur_{Exp} = date_{Last} - date_{First} + d_{int}$$

where d_{int} represents the dosing interval of 14 days.

The cumulative duration of exposure will be summarized for subjects exposed for at least one day, ≥ 183 days, ≥ 365 days, ≥ 548 days, ≥ 730 days.

Additionally, the subject time at risk will be summarized. Subject time at risk (in days) is calculated as:

$$T_{Risk} = date_{Last} - date_{First} + (5 * t_{1/2})$$

where $t_{1/2}$ is 14 days.

If there is a change of treatment or the last clinical contact occurs prior to completion of the follow-up period, the date of last clinical contact per subject is defined as the maximum of [last visit date including safety follow-up visits, last imputed AE start date, last date of termination or completion, last date of study drug administration, death date] or the clinical cutoff date for ongoing studies if earlier than this maximum date).

In cases where the date of last clinical contact (LastCC) occurs prior to completion of this follow-up period, subject time at risk (in days) will be calculated as:

$$T_{Risk} = date_{LastCC} - date_{First} + 1$$

Subject years at risk is the sum of all relevant subject time at risk (in days) divided by 365.25.

The study medication duration will be listed together with the dates of first and last study medication administration.

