10.2 Adverse events

Adverse events with start date prior to first administration of study medication are defined as pre-treatment AEs. No summaries of these events will be produced although they will be included in listings.

Adverse events that started more than 70 days after the last administration of study medication are defined as post-treatment AEs. Such events will not be included in tabulated summaries, but will be listed.

Treatment emergent AEs are all AEs starting on or after the date of first study medication and up to 70 days after the last (most recent) dose of study medication. AEs occurring more than 70 days after the last (most recent) dose will not be considered treatment emergent, regardless of whether this occurs during the safety follow-up period, or after a treatment gap of more than 70 days.

If a start date is missing, then the AE will be considered a treatment emergent adverse event (TEAE). Duration should not be calculated if there is missing stop date information.

If the intensity of an adverse event is unknown, it is considered as severe. If the relationship to study drug is missing, it is considered as related.

Tables showing TEAEs, serious TEAEs, non-serious TEAEs, TEAEs leading to discontinuation of study drug, TEAEs by maximum intensity, TEAEs by relationship, serious TEAEs by relationship, fatal TEAEs by relationship, TEAEs including subject numbers will be provided on the SS.

Additionally, more detailed summaries of TEAEs will be presented, which include the exposure adjusted incidence rate (EAIR) with associated 95% confidence interval, and the exposure adjusted event rate (EAER).

The EAIR is defined as the number of subjects (n) with a specific AE adjusted for the exposure and will be scaled to 100 patient-years:

$$EAIR = 100 \cdot n / \sum_{i=1}^N T_{Exp,i}$$

If a subject has multiple events, the time of exposure is calculated to the first occurrence of the AE of interest. If a subject has no events, the total time at risk is used.

Exact Poisson 95% confidence intervals for incidence rates are calculated using the relationship between the Poisson and the Chi-square distribution (Ulm, 1990):

$$LCL = \chi_{2n, \alpha/2}^2 / 2$$

$$UCL = \chi_{2(n+1), 1-\alpha/2}^2 / 2$$

where n is the number of subjects with a specific AE for the incidence rate of interest and is the basis for the number of the degrees of freedom for the chi-square quantile for the upper tail probability χ^2 .

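### At the Week 48 interim, AE counts stop at the Week 48 Visit, but the time-at-risk rule as written does not, so non-zero exposure-adjusted rates would be biased low

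*SAP*

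**What the plan says.** **Events.** SAP 4.3 restricts the interim AE tables: "Summary tables of results not provided by visit, e.g. adverse events, will not include events or medication that started after the Week 48 Visit". The next sentence is broader: "Data collected after Week 48 will not be presented in the interim analysis". Earlier in the same paragraph, however, the SAP says: "All data collected until the database cut-off date will be included".

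**Time at risk.** SAP 10.1 defines it as last dose minus first dose plus 70 days (five half-lives of 14 days). If last clinical contact comes sooner, it is last contact minus first dose plus 1 day. Last contact is the latest of several dates (visit, AE start, termination or completion, dose, death), "or the clinical cutoff date for ongoing studies if earlier than this maximum date". Week 48 is not mentioned.

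**Rates.** In SAP 10.2 the EAIR uses time to first event for subjects with the event. For the others: "If a subject has no events, the total time at risk is used". The EAER divides all events by the total time at risk of all subjects.

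**Default rule.** SAP 4.3: "In general, the interim analysis will follow the same specifications as the final analysis, unless stated differently in the corresponding sections". Sections 10.1 and 10.2 state nothing different for the interim.

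**Flares, for contrast.** SAP 8.1.1 sets the interim on-study offset for a subject who reaches the Week 48 Visit at 336 days, so flare counts and flare time cover the same window.

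**The concern.** A rate per 100 patient-years is valid only if events and person-time come from the same window. The interim takes place once the last subject has reached Week 48, so subjects enrolled earlier are by then well past it. Their later AEs are left out, while section 10.1 as written still counts their later time. The error can go in one direction only: non-zero rates look lower, and therefore more reassuring, than they should.

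TEAEs are the secondary safety variable (SAP 2.2.2.1). The interim gives first results about a year before the final analysis, and no data monitoring committee is planned (SAP 4.3). Interim rates built this way would also not be comparable with the final rates, which have no Week 48 cut.

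**Working it through.** The documents give no interim AE rate or person-time, so there is no figure of the plan's own to reproduce. The check applies the 10.1 and 10.2 formulas to the planned schedule.

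**Inputs**
- End of event counting: Week 48, day 336 (SAP 4.3; 336 days as in 8.1.1). Matched time at risk: 336 + 1 = 337 days.
- Recruitment: about 12 months (Protocol 5.1.2), taken as 365 days.
- Doses every 14 days, the last at Week 94 = day 658.
- Assumptions: uniform accrual, no dropout, constant event rate, and a cutoff at the last subject's Week 48 Visit. The SAP gives no calendar date for the cutoff.

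**Reading A: 10.1 as written, time running to the cutoff.** The gap from a subject's own Week 48 Visit to the cutoff is uniform on 0 to 365 days, mean 182.5. The 70-day limit never applies: the first subject enrolled has 336 + 365 + 1 = 702 days, below 658 + 70 = 728. Mean time at risk is 337 + 182.5 = 519.5 days. EAER ratio to the matched rate: 337 / 519.5 = 0.65 (in weeks, 48 / (48 + 26) = 0.65).

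**Reading A2: time ending at the last scheduled visit before the cutoff.** The later visits are at Weeks 60, 72, 84 and 96, that is 84, 168, 252 and 336 days after Week 48. Mean extra time is (84×84 + 84×168 + 84×252 + 29×336) / 365 = 142.7 days. The ratio is 337 / 479.7 = 0.70. This treats home doses since that visit as not yet recorded.

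**Reading B: doses cut at Week 48, 70-day tail kept.** Time at risk is at most 336 + 70 = 406 days, so the extra time is the smaller of 69 days and the gap. Its mean is 69 − 69² / (2×365) = 62.5 days. The ratio is 337 / 399.5 = 0.84.

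**Reading C: all dates cut at Week 48.** Time at risk is 337 days and the ratio is 1.00.

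**EAIR under reading A.** With event rate λ per year, let p = 1 − exp(−λ × 337/365.25). Matched person-time per subject is p/λ. The excess falls only on event-free subjects: (1 − p) × 182.5/365.25 = (1 − p) × 0.4997. The ratio is (p/λ) / [p/λ + (1 − p) × 0.4997].

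| True rate per 100 PY | p | p/λ | Excess | Ratio |
|---|---|---|---|---|
| 10 | 0.088 | 0.881 | 0.456 | 0.66 |
| 50 | 0.370 | 0.739 | 0.315 | 0.70 |
| 100 | 0.603 | 0.603 | 0.199 | 0.75 |
| 300 | 0.937 | 0.312 | 0.031 | 0.91 |

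As λ falls the ratio tends to the EAER value; at 1 per 100 PY it is 0.65.

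**Other accrual lengths (reading A, EAER).**
- 3 months: 337 / 382 = 0.88.
- 6 months: 48 / 61 = 0.79.
- 18 months: extra time is uniform on 0 to 78 weeks, capped at 56 (Week 104). Its mean is (56²/2 + 22×56) / 78 = 35.9, so the ratio is 48 / 83.9 = 0.57.

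A simulation of 400,000 subjects agrees with these values. With 15% dropout by Week 96 and 12-month accrual it gives 328 / 494 = 0.66.

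**The case against.** The strongest reply is that section 4.3 already settles the matter: "Data collected after Week 48 will not be presented in the interim analysis". Dose and visit dates after Week 48 are data collected after Week 48. If they are left out, last contact becomes the Week 48 Visit, time at risk is 337 days and the mismatch disappears (reading C). The rationale for SAP Amendment 1 points the same way, since it says that the interim will use data up to Week 48 only.

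This reading is open, and it stands as a reason not to treat the bias as established. It does not close the gap, for three reasons. The same paragraph says "All data collected until the database cut-off date will be included". Section 10.1 does provide for ongoing studies, and the limit it names is the clinical cutoff date. For flares, the plan did not rely on the general sentence but wrote out the 336 days.

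A reader might infer more than the documents support:
- *That every interim rate is understated.* Zero rates do not change. Subjects whose time at risk ends by Week 48, or whose Week 48 Visit falls at the cutoff, add no mismatch. Common-event EAIRs are less affected.
- *That a regulatory submission would carry the error.* SAP 4.3 mentions a possible additional data-cut for that purpose. Nothing says that the Week 48 rule for AEs governs it.
- *That stopping decisions or safety monitoring are at risk.* The interim has no efficacy or futility stopping rule, and safety data are monitored separately under the signal-detection charter.

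Subject counts and percentages do not use this denominator. The interim contains only a subset of tables, marked in display specifications that are not available here, so whether EAIR and EAER are among them is unknown.

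**Conclusion.** The point holds as an unmatched denominator in the text, not as a demonstrated bias in results. SAP 4.3 ends the interim AE count at the Week 48 Visit. SAP 10.1, carried over by the default rule, lets time at risk run on. Followed as written, this biases non-zero exposure-adjusted rates downward; no reading examined biases them upward.

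Under the stated assumptions on accrual, dropout and cutoff, the EAER and rare-event EAIR are 0.65 of the matched rate, 35% too low. Depending on how the end of time at risk is read, the ratio is 0.65, 0.70, 0.84 or 1.00, so the choice of reading matters as much as the length of recruitment. The final analysis is unaffected, and the point has no practical effect if the interim tables omit these rates.

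**What to change.** Add to SAP 10.1, with a cross-reference in 10.2: for the Week 48 interim, time at risk and exposure are censored at the earliest of the Week 48 Visit date, last dose plus 70 days, and last clinical contact. A subject with no Week 48 Visit keeps the other two limits. This matches the AE counting window, as 8.1.1 already does for flares.

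The cost is one sentence and one change to the time-at-risk derivation for the interim. If time at risk had been run past Week 48, the interim rates would rise, by a factor of 519.5 / 337 = 1.54 for the EAER under reading A. If interim outputs already exist, the sponsor should confirm which denominator was programmed and state it with the tables. Counting all AEs to the cutoff would also align the two windows, but it would reverse the Week 48 restriction that Amendment 1 introduced on purpose, so it is not recommended.

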4.4 Multicenter studies

The data from all centers will be pooled for the purposes of the final analyses. There will be no formal statistical evaluation of the effect of center on the results obtained.

4.5 Multiple comparisons/multiplicity

Although there is no intention to stop the study early due to efficacy or futility on the basis of the interim results, $\alpha=0.001$ will be spent in conjunction with this formal interim review of the data (Haybittle, 1971), and the final analysis of the primary efficacy variable will be conducted at the reduced 2-sided α -level of 0.049.

4.6 Use of an efficacy subset of subjects

Not applicable.

4.7 Active-control studies intended to show equivalence

Not applicable.

4.8 Examination of subgroups

The primary efficacy variable will be summarized using the following subgroups:

- Gender (Male, Female)
- Age (<median, >=median)
- axSpA subpopulation as determined by the investigator (Ankylosing Spondylitis, non-radiographic axial spondyloarthritis)

A Poisson regression model as described for the primary analysis will be used including terms for the subgroup and the subgroup by treatment period interaction. The results will be presented, but no p-values will be given.

5 STUDY POPULATION CHARACTERISTICS

5.1 Subject disposition

Subject disposition will be listed for all subjects screened and will include the following information: subject status (screen failure, completed or discontinued), date of informed consent, date of first and last dose of study medication (including relative day for last dose), date of premature study termination (if applicable) and primary reason for study termination (if

applicable). For screen failures the date and reason for screen failure will be listed. Subject disposition will be summarized for all subjects screened including the reasons for screen failure. Subject disposition will also be summarized for the Enrolled Set including the reasons for discontinuation of study and/or study medication. Study eligibility criteria will be listed and a separate listing of subjects who did not meet the eligibility criteria will be presented. A listing of study visit dates will be presented by subject including the relative study day with respect to treatment start for each visit.

5.2 Protocol deviations

Protocol deviations will be identified and documented as described in [Section 3.4](#). The assignment of subjects to each of the analysis sets will be listed for all subjects screened. In addition, a listing of subjects excluded from the analysis sets will be presented including the reasons for exclusion; this listing will be based on the Enrolled Set.

6 DEMOGRAPHICS AND OTHER BASELINE CHARACTERISTICS

6.1 Demographics

Tables with descriptive statistics and listings will be given for the demographic variables age (at time of informed consent), gender, weight and height at Baseline, race, ethnicity, body mass index (BMI), and body surface area (BSA) as calculated below. Demographic characteristics will be summarized for the SS.

Only the year of birth has been collected, so the age will be calculated with the documented year of birth, January as imputed month and 1 as imputed day of birth, at the time of informed consent, as follows:

$$\text{Age (years)} = ([\text{Date of Informed Consent}] - [\text{Imputed Date of Birth}]) / 365.25$$

It will be summarized as a continuous variable and as a categorical variable based on the following 3 categories: ≤ 18 years, >18 and <65 years, ≥ 65 years.

The BMI will be calculated using the following formula (Keys et al, 1972):

$$\text{BMI (kg/m}^2\text{)} = 10000 * \frac{\text{weight (kg)}}{[\text{height (cm)}]^2}$$

The BSA for adults is calculated using Mosteller's formula (Mosteller, 1987):

$$\text{BSA (m}^2\text{)} = \sqrt{\frac{\text{height (cm)} \times \text{weight (kg)}}{3600}}$$

6.2 Other Baseline characteristics

Disease duration of axSpA will be calculated as the difference between the date of Baseline visit and the onset date of axial spondyloarthritis (axSpA) or Ankylosing spondylitis (AS) as documented on the medical history pages. If the onset date of axSpA is partial, it will be imputed to the most recent feasible date (ie, first day of the month if only day is missing, or the first day of the year if day and month are missing). Disease duration of axSpA will be summarized as continuous variable in years, as well as categorized into <2 years and ≥ 2 years.

Time since onset of first uveitis flare will be calculated as the difference between the date of Baseline visit and the onset date of first uveitis flare. If the onset date of first uveitis flare is partial, it will be imputed to the most recent feasible date (ie, first day of the month if only day is missing, or the first day of the year if day and month are missing). Time since onset of first uveitis flare will be summarized as continuous variable in years, as well as categorized into <2 years and ≥ 2 years.

Other baseline characteristics include number of subjects with IBD, number of subjects with psoriasis, number of subjects with at least one tender joint, and number of subjects with at least one swollen joint.

Data collected on childbearing potential will be listed, which includes the method of birth control if the subject is a female of childbearing potential, or if the subject is a fertile male. Also the reason why a male subject is not fertile, or why a female is not of childbearing potential is displayed.

Lifestyle data shows the use of alcohol, caffeinated beverages, illicit drugs, and tobacco. The categories will be summarized on the SS. For subjects with former or current tobacco use, the duration of use is collected and summarized, as well as the number of daily cigarettes, cigars, chewing tobacco, and pipes.

The responses to the following modified ASAS classification criteria for AS will be summarized for all subjects in a frequency table using the SS:

- Back pain of ≥ 3 months and subject's age at onset <45 years
- Inflammatory back pain
- Reactive arthritis
- Enthesitis
- Uveitis
- Dactylitis
- Psoriasis
- Inflammatory bowel disease
- HLA-B27
- Elevated CRP (above upper limit of normal)
- Sacroiliitis

If medical history terms of back pain or inflammatory back pain are missing for a subject, then the terms axial spondyloarthritis or Ankylosing spondylitis will be used instead.

6.3 Medical history and concomitant diseases

The Medical history contains any previous or ongoing medical conditions that occurred prior to study entry. They will be listed for all subjects in the SS including the reported term, start date (month and year only), end date (month and year only) (or ongoing if applicable) and the information whether the procedure is related to axSpA. A glossary of all medical conditions will

also be presented including the reported term, the preferred term and the System Organ Class. The classification of medical history will be done according to the MedDRA coding system using system organ class (SOC) and preferred term (PT). These data will be summarized using frequency tables for subject count by classified data.

Procedure history will be displayed in a listing only, data will not be coded.

Extra-articular assessments of psoriasis, IBD, reactive arthritis and uveitis will be presented in listings, based on the subjects in the SS.

6.4 Prior and concomitant medications

Prior medications include any medications that started prior to the start date of study medication. Past medications are a subset of prior medications and include prior medications with a stop date before the date of first study medication administration.

Concomitant medications will be assigned to the treatment period according to whether they were taken at least one day in common with the study medication in that period. That is, if the start or end date of the concomitant medication is on or between the first study drug administration date and the last study drug administration date plus 14 days, or, if the concomitant medication starts prior to first study drug administration and ends after the last study drug administration date plus 14 days.

Concomitant medications will be assigned to the follow-up period if the start date of the concomitant medication is after the last study drug administration date plus 14 days.

A medication can be defined as both prior and concomitant. Where a medication start or stop date is (partially) missing, the medication will be considered a concomitant medication, unless the partial data is suggesting otherwise. Imputation of dates will follow the rules described in section [Section 4.2](#). Concomitant medications will be summarized for subjects in the SS. The following information will be included in the listings: reported term, dose per intake and dose unit, frequency, formulation, route, indication, start and stop dates (including relative study day), and in case of missing stop date, the information whether the intake of medication is ongoing.

Past medication summaries will be generated for disease-modifying antirheumatic drugs (DMARDs), non-steroidal anti-inflammatory drugs (NSAIDs), and anti-tumor necrosis factors (anti-TNFs) by anatomical therapeutic chemical (ATC) Anatomical Main Group (ATC Level 1), Pharmacological Subgroup (ATC level 3), and PT).

Concomitant DMARDs and NSAIDs will be summarized by WHO-DD Anatomical Main Group (ATC Level 1), Pharmacological Subgroup (ATC level 3), and PT). Concomitant medications other than DMARDs and NSAIDs will also be summarized.

Intake of any new prohibited medication since last visit is collected and presented in a separate listing.

7

MEASUREMENTS OF TREATMENT COMPLIANCE

There will be 2 approaches to calculate treatment compliance. The first will utilize the number of administered syringes and compare them to the scheduled expected number of syringes. Two syringes should be administered for the loading doses (at weeks 0, 2 and 4) however only 1 syringe should be administered at any other visit from Week 6 until Week 94/last scheduled

injection. The difference in number of syringes between the total actual used and the total expected syringes will be summarized. In addition, a ratio of compliance will be further computed based on the number of actual and expected syringes. The ratio of compliance will be summarized as a continuous variable and categorically (<0.80, ≥0.80-≤1.0 and >1.0). The general formula for the compliance ratio (CR) is given as follows:

$$CR = \frac{N_{Syr_act}}{N_{Syr_exp}}$$

where N_{Syr_act} is the number of actual injections and N_{Syr_exp} is the number of expected injections. The second approach defines compliance with study drug administration based upon comparing the actual day of administration with the expected day of administration. The expected day of administration will be based upon the Baseline date and the previous injection date. The sum of the absolute difference in days between the actual and expected days will be summarized. In addition, a ratio of compliance will be further computed based upon the actual and expected day. The ratio of compliance will also be summarized as a continuous variable and categorically (<0.80, ≥0.80-≤1.0 and >1.0). The general formula for the compliance ratio based on duration (CRD) is given as follows:

$$CRD = \frac{T_{Dur_stu} - \Delta_{Cum}}{T_{Dur_stu}}$$

where T_{Dur_stu} is the study duration and Δ_{Cum} is the cumulative difference between actual and scheduled day of administration.

Specific details of this formula are provided in [Appendix 12.1](#) (Compliance Ratio Calculation).

The CRD ranges between 0 and 1. To calculate study duration, the date of the Week 94 visit or the last injection date prior to study treatment discontinuation will be compared to the Baseline date, as shown below:

Study Duration (days) = Week 94 visit/last injection date – Baseline date + 14

The sum will be calculated for the 11 visits from Week 0 (Baseline) to Week 84, and for all planned home administrations from week 6 to week 94. In case the actual day of administration is missing, the maximum deviation to the scheduled day will be assumed (ie, 14 days). If, for a scheduled day with 2 planned injections, the syringes were administered on 2 different days, the maximum day difference of the 2 actual dates to the scheduled date will be utilized.

